## 5 GENERAL CONSIDERATIONS

### 5.1 Sample Size

For the primary endpoint analysis of the percent change of 7-day average daily peak pruritus NRS from Baseline to Week 4, N = 24 / group will give us 80% power to detect a standardized effect of 0.72 with 2-sided significance level of 0.1 (28.8% improvement over placebo in % change from baseline in pruritus, assuming standard deviation [SD] = 40%).

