Mean and variance estimation: A MMRM model with visit, treatment and visit by treatment interaction as fixed effects, baseline NRS as covariate, participant as random effects will be fitted first, the ls means and their variance-covariance matrix at Week 4 will be estimated using the fitted model.

1. MCP-step: the candidate models are tested using the estimated means and their variance- covariance matrix from the previous step. If any of the models is statistically significant at two-sided significance level of 0.1, the treatment effect is established, the analysis moves to the next step.
2. Mod-step: the concentration-response curve will be characterized, and the minimum effective concentration and optimal concentration will be estimated. All significant models indicated by the previous step will be fitted, and minimum effective concentration and optimal concentration will be estimated based on the fitted models.
3. Finally, weighted estimates for minimum effective concentration and optimal concentration will be calculated using weighing in Buckland et al. (Buckland 1997).

For MMRM model fitting, the unstructured (UN) variance-covariance matrix will initially be assumed. If the model does not converge using the UN covariance structure, the autoregressive (order 1) AR(1) structure will be used. If the AR(1) structure also does not converge, other covariance structures, such as the Toeplitz structure, deemed appropriate to fit the data will be used.

To estimate the degree of freedom, the Kenward Roger method will be used.

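### The primary MMRM names a redundant participant random effect, and its first covariance fallback, AR(1), assumes equal variance at every week. If that fallback were used and variances differed by week, the Week 4 standard errors sent to MCPMod would be wrong in either direction.

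*SAP*

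**What the plan says.** SAP 13.1 builds the primary analysis on an MMRM with visit, treatment and their interaction, and with "baseline NRS as covariate, participant as random effects will be fitted first". On the covariance it says that "the unstructured (UN) variance-covariance matrix will initially be assumed". It then gives two fallbacks. The first is "If the model does not converge using the UN covariance structure, the autoregressive (order 1) AR(1) structure will be used". If that also fails, "other covariance structures, such as the Toeplitz structure, deemed appropriate to fit the data will be used". On inference it adds: "To estimate the degree of freedom, the Kenward Roger method will be used". No structure with week-specific variances is named apart from UN, and no robust (sandwich) variance is mentioned.

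The fit feeds the primary test directly: "the ls means and their variance-covariance matrix at Week 4 will be estimated using the fitted model", and these go into the MCP step, where "If any of the models is statistically significant at two-sided significance level of 0.1, the treatment effect is established".

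Protocol 9.3.1 also names participant as a random effect, both for the primary model and for the NRS change analyses, but gives no covariance structure. SAP 13.2 repeats the random-effect wording for the continuous secondary endpoints. SAP Appendix 2 lists the packages mmrm, nlme and lme4 but shows no code for the MMRM. SAP 15 does not mention the point.

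**The concern.** A participant random intercept adds one constant to every element of the within-participant covariance matrix. A UN matrix already estimates every element freely, so the two cannot be told apart. The model as worded is over-parameterised, and software that tries to fit both may report a singular fit or stop.

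The written response to non-convergence is AR(1), which in its usual form has one variance for all four weeks and one correlation. It is a special case of the Toeplitz structure that the plan reaches only afterwards. Ordinary Toeplitz shares the equal-variance assumption, and so does a plain random-intercept model, which is how Protocol 9.3.1 reads on its own.

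An equal-variance fit gives Week 4 roughly the average variance over Weeks 1 to 4. If the spread of percent change differs by week, the Week 4 standard error is wrong. That error passes straight into the two-sided 0.1 test and the later dose-response fits. Kenward-Roger adjusts for sample size and does not repair a wrong structure.

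**Working it through.** **Inputs from the documents.** Week 4 SD 40, difference 28.8, 24 per group, two-sided 0.1 (SAP 5.1). Four weekly averages, NRS Weeks 1 to 4 (SAP 5.7.2). Four arms, 1:1:1:1, about 120 enrolled (SAP 3.1), so 4 × 24 = 96 to 120 participants.

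**Assumptions.** SDs for Weeks 1 to 3, which the documents do not give; correlation 0.8 between adjacent weeks; complete data.

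**1. The plan's own figure.** SAP 5.1 states that "N = 24 / group will give us 80% power to detect a standardized effect of 0.72 with 2-sided significance level of 0.1". Standardized effect: 28.8/40 = 0.72. n = 2(1.645 + 0.842)²/0.72² = 12.37/0.5184 = 23.9, so 24 per group. Power at 24 is 0.802, and the six-shape MCP test gives 0.804 to 0.850. The figure is reproduced and is not affected by what follows.

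**2. Is the random effect harmful in itself?** Total covariance = R + σ_b²J, where J is a matrix of ones. Take SDs 25/30/35/40. With σ_b² = 0, 50 or 150, set the Week 4 element of R to 1600, 1550 or 1450 and reduce the other elements likewise. R stays positive definite, and the Week 4 total is 1600 each time. Only the split is undetermined. The total covariance, and so the Week 4 means and standard errors, are the same.

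**3. Is non-convergence to be expected?** UN for four visits has 4 × 5/2 = 10 parameters. REML fits were simulated with SDs 25/32/37/40, at 24 per arm with no dropout and at 24 and 30 per arm with an assumed 20% dropout. UN alone converged in 120 of 120 datasets, and so did UN plus the redundant effect. The Week 4 standard errors agreed to within 0.001%. This used one optimiser with good starting values, so other software may behave differently.

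**4. Size of the error if AR(1) is used.** True standard error of a difference: 40 × √(2/24) = 11.55. Hand check of the ratio r = (model SE)/(true SE): r ≈ √(mean variance/1600).

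- 32/35/38/40: (1024 + 1225 + 1444 + 1600)/4 = 1323.25; r ≈ 0.91
- 25/32/37/40: (625 + 1024 + 1369 + 1600)/4 = 1154.5; r ≈ 0.85
- 20/28/35/40: (400 + 784 + 1225 + 1600)/4 = 1002.25; r ≈ 0.79
- 50/47/44/40: (2500 + 2209 + 1936 + 1600)/4 = 2061.25; r ≈ 1.14

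The best-fitting AR(1) was then found for each profile. The MCP test rejects when the largest of the six absolute contrast statistics exceeds about 1.96. With a wrong SE, the effective cut-off is 1.96r.

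| Assumed SDs, Weeks 1–4 | r under AR(1) | Model SE (r × 11.55) | MCP-step level, large sample | MCP-step level, simulated AR(1) REML fits |
|---|---|---|---|---|
| 40/40/40/40 | 1.00 | 11.55 | 10% | – |
| 32/35/38/40 | 0.91 | 10.5 | about 15% | 14.3% |
| 25/32/37/40 | 0.84 | 9.7 | about 19% | 18.3% |
| 20/28/35/40 | 0.79 | 9.1 | about 22% | 21.9% |
| 50/47/44/40 | 1.13 | 13.1 | about 5.5% | – |

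**5. Would the other listed routes help?** For a similar set of SD profiles, ordinary Toeplitz and a participant random intercept with AR(1) gave ratios within 0.004 of AR(1). Reordering the fallbacks is therefore not enough; the variances must be allowed to differ by week.

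**The case against.** The strongest reply is that the phrase about participant as a random effect is loose wording for participant as the grouping unit. SAP 13.1 calls the model an MMRM and starts from UN, so the natural reading is the standard UN model. With four weekly values and 96 to 120 participants, that model should converge and the fallback would not be reached. This largely stands, and it is why the point is graded low.

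A reader might infer that the model as written has no unique fit, so that the Week 4 standard errors are already unreliable. The documents do not support that: step 2 shows that everything passed to MCPMod is uniquely determined. A reader might also infer that non-convergence is likely. Nothing in the documents shows this, and the simulation in step 3 did not produce it.

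Third, a reader might infer that the primary test will reject too often. That needs an equal-variance structure to be used and the SD to rise over the weeks. No SD is stated for Weeks 1 to 3, and a falling profile makes the test conservative.

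Two smaller objections also stand. AR(1) is not uniquely restrictive, since compound symmetry has two parameters as well. And the open final fallback does not exclude structures with unequal variances. That openness still leaves a primary-analysis choice to be made after the data have been seen.

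The written rule is untouched by these replies. When triggered, it selects an equal-variance structure first, with no robust variance, for the primary test.

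**Conclusion.** The point holds as a low-probability safeguard, not a must-fix. The random effect is redundant alongside UN and does no numerical harm when the fit succeeds. The weakness is the fallback. If AR(1), ordinary Toeplitz or a plain random-intercept model is used and variance differs by week, the Week 4 standard error is wrong in a direction that cannot be known in advance.

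Given the fallback, the assumed profiles put the standard error between 21% too small and about 13% too large, and the MCP-step level between about 22% and about 5.5% against a nominal 10%. With flat SDs there is no error. These figures rest on assumed SDs for Weeks 1 to 3, adjacent-week correlation 0.8, 24 per arm and complete data. With dropout, a wrong covariance could also shift the Week 4 means; that was not computed.

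**What to change.** In SAP 13.1 and 13.2, remove the phrase naming participant as a random effect. State a UN within-participant covariance with participant as the grouping unit. Record this in SAP 15 as a clarification of Protocol 9.3.1.

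Replace the fallback by a closed, ordered list with week-specific variances: heterogeneous Toeplitz, then heterogeneous AR(1), then heterogeneous compound symmetry. Keep Kenward-Roger for these. If a sandwich variance is preferred, name the degrees-of-freedom method that goes with it.

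The cost is SAP text and the matching model code, settled before unblinding. Data, visits and the sample size do not change. The only statistical cost arises if the fallback is used: for four visits, heterogeneous Toeplitz has 4 + 3 = 7 covariance parameters and heterogeneous AR(1) or compound symmetry has 4 + 1 = 5, against 2 for AR(1).

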### **13.1.1 The Primary Analyses – Percent Change of 7-day Average of the Peak Pruritus NRS at Week 4**

The primary analysis of the primary efficacy end point is the percent change of 7-day average of the peak pruritus NRS as defined in [section 5.7.3](#) using the analysis method described in [section 13.1](#) using the mITT analysis set.

### **13.1.2 The Sensitivity Analyses – Percent Change of the All Available 7-day Average of the Peak Pruritus NRS at Week 4**

The percent change of all available 7-day average of the peak pruritus NRS as defined in [section 5.7.4](#) will be repeated using method described in [section 13.1](#) using the mITT analysis set as a sensitivity analysis. In addition, both the percent change of 7-day average of the peak pruritus NRS and the all available 7-day average of the peak pruritus NRS analyses will be repeated using the PP set.

## **13.2 Key Secondary Endpoints**

The following continuous secondary efficacy endpoints, as defined in [section 5.7](#), will be analyzed using MMRM model with visit, treatment and visit by treatment interaction as fixed effects, baseline NRS as covariate, participant as random effects will be fitted first, the ls means and their variance-covariance matrix at Week 4 will be estimated using the fitted model. Percent change of 7-day average daily peak pruritus NRS from Baseline to Week 1, 2, and 3.

- Change of 7-day average daily peak pruritus NRS from Baseline to Week 1, 2, 3 and 4.
- Change and percent change from baseline in daily peak pruritus NRS from Days 1 to 7.
- Change from baseline in 5-D Pruritus Scale at Week 2 and 4.
- Change and percent change from baseline in the EASI score at Week 2 and 4.
- Change from baseline in total BSA at Week 2 and 4.
- Change from baseline in the Dermatology Life Quality Index (DLQI) at Week 2 and 4.
- Change from baseline in The Patient Oriented Eczema Measure (POEM) at Week 2 and 4.

The endpoints will be summarized by visit presenting LS Mean, 95% CI and associated p-value from the above MMRM model, using mITT analysis set and PP set.

The following categorical secondary efficacy endpoints will be analyzed based on Fisher's exact test. In addition, odds ratio (OR) and 95% Wald confidence intervals will also be presented when applicable:

- Pruritus response is defined as the 7-day average of daily peak pruritus NRS reduction  $\geq 4$  points from Baseline at Week 1, 2, 3, and 4.

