7.1. Peak Pruritus Numerical Rating Scale

The Peak Pruritus NRS is a single self-reported item designed to measure peak pruritus, or ‘worst’ itch, over the previous 24 h based on the following question: ‘On a scale of 0 to 10, with 0 being “no itch” and 10 being “worst itch imaginable”, how would you rate your itch at the worst moment during the previous 24 hours?’

Participants will be trained on completion of the Peak Pruritus NRS scale at the first Screening Visit before the Peak Pruritus NRS measurements for eligibility are collected.

To be eligible for this study, participants must have a pruritus NRS score of ≥ 7 at screening and Day 1.

On Day 1, pruritus NRS will be assessed at several time points: pre-dose to confirm eligibility and then hourly in the eDiary starting immediately post-dose until bedtime. Following Day 1, participants will record the peak pruritus NRS daily in the eDiary before the morning investigational product application, and their compliance on the peak pruritus NRS will be followed at each clinic visit.

During study visits, the NRS data will be recorded by site staff in the eCRF.

7.2. 5-D Pruritus Scale

The 5-D Pruritus Scale is a 1-page, 5-question, validated questionnaire used in clinical trials to assess 5 dimensions of background itch: degree, duration, direction, disability, and distribution. Each question corresponds to 1 of the 5 dimensions of itch; participants will rate their symptoms over the preceding 2-week period as “present” or on a 1 to 5 scale, with 5 being the most affected. The 5-D Pruritus Scale will be recorded at the visits specified in [Table 2](#).

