7.5. Body Surface Area Involvement of Atopic Dermatitis

The overall BSA affected by AD (total BSA) will be evaluated (from 0% to 100%) at the visits specified in [Table 2](#). The palmar surface of one hand represents 1% of participant's total BSA. In addition, at the screening and Day 1 visits, the BSA will be evaluated to verify each participant's eligibility, but excluding palms, scalp, axillae, groin, genitals, and folds. In addition, the BSA of treated area (include active, cleared, and new lesions) will be calculated at the visits specified in [Table 2](#). The BSA of treated area will be used to calculate the number of FTUs to be applied by participants on AD lesions (except on scalp, axillae, groin, and genitals, and folds), with a maximum treated area of approximately 20% BSA. If new lesions on the soles of the feet appear after Day 1 and initiation of treatment, then these lesions should be excluded from the BSA of treated area (should not be treated).

To be eligible, participants must have a BSA (excluding palms, scalp, axillae, groin, genitals, and folds) of 1-20% at Day 1 visit. In addition, participants with presence of AD on soles at screening or Day 1 and participants with a ratio of BSA of intended area over total BSA of less than 80% on Day 1 will be excluded.

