### 5.2 Baseline

Unless otherwise specified, baseline value will be defined as the last non-missing assessment prior to or on the first study treatment application date and time (including unscheduled assessments). If the last non-missing assessment is performed on the same date as the first study treatment and time is not available, the assessment will be considered as baseline, except for adverse events (AEs) and medications starting on the first study treatment dose date, which will be considered post-baseline.

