### 5.4 Descriptive Statistics

All continuous variables will be summarized by the number of participants, mean, SD, median, minimum, and maximum. Categorical variables will be presented as frequencies and percentages. Summary tables will be presented by treatment and visit, when applicable.

- Change from baseline will be calculated as:
  - Assessment value at post-baseline visit X – baseline value.
- Percent change from baseline will be calculated as:
  - $(\text{Assessment value at post-baseline visit X} - \text{baseline value}) / \text{baseline value} \times 100$ .

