#### **5.7.5 5D-Pruritus Scale**

The 5-D Pruritus Scale is a 1-page, 5-question, validated questionnaire used in clinical trials to assess 5 dimensions of background itch: degree, duration, direction, disability, and distribution.

Each question corresponds to 1 of the 5 dimensions of itch; subjects will rate their symptoms over the preceding 2-week period as “present” or on a 1 to 5 scale, with 5 being the most affected.

The scores of each of the five domains are achieved separately and then summed together to obtain a total 5-D score. 5-D scores can potentially range between 5 (no pruritus) and 25 (most severe pruritus). The score will be set to missing in case where at least one of the five domain results is missing.

- Single-item domain scores (duration, degree, and direction) are equal to the value in the response choice (range 1–5).
- The disability domain includes four items that assess the impact of itching on daily activities: sleep, leisure/social activities, housework/errands, and work/school. The score for the disability domain is achieved by taking the highest score on all available items.
- For the distribution domain, the number of affected body parts is tallied among all available items (potential sum 0–16) and the sum is sorted into five scoring bins: sum of 0–2 = score of 1, sum of 3–5 = score of 2, sum of 6–10 = score of 3, sum of 11–13 = score of 4, and sum of 14–16 = score of 5.

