**Week 2 and 4.**

The following continuous exploratory efficacy endpoints will be analyzed using an MMRM model similar to the continuous secondary efficacy endpoints:

- Change from baseline in vIGA at Weeks 2 and 4.

The following exploratory endpoint will be summarized and listed using mITT analysis set and PP set:

- Hourly Pruritus Numeric Rating Scale (NRS) on Day 1.

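### SAP 13.2 adjusts change in 5-D, EASI, total BSA, DLQI and POEM for baseline NRS only; adding each endpoint's own baseline costs about one degree of freedom and gains precision unless its slope is near 1

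*SAP*

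**What the plan says.** SAP 13.2 specifies a single MMRM for all its continuous secondary endpoints: visit, treatment, "visit by treatment interaction as fixed effects, baseline NRS as covariate, participant as random effects will be fitted first". Eight endpoints fall under it. Three are NRS measures. The other five are change in 5-D, EASI (also as percent change), total BSA, DLQI and POEM, for example "Change from baseline in the Dermatology Life Quality Index (DLQI) at Week 2 and 4".

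Each of the five has a defined baseline. SAP 5.2 states that "baseline value will be defined as the last non-missing assessment prior to or on the first study treatment application date and time", which is normally the Day 1 value. The schedule of events places 5-D, EASI, DLQI and POEM on Day 1. Its BSA row is for BSA with certain sites excluded, but Protocol 7.5 also requires total BSA at the scheduled visits. SAP 5.4 defines change as the post-baseline value minus baseline.

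No SAP section puts these baselines into the model, and SAP 15 lists no change on the point. Protocol 9.3.1 says only that other continuous variables are handled like the NRS percent-change analysis, whose covariate is baseline pruritus NRS. For the exploratory vIGA change, SAP 13.3 says: "The following continuous exploratory efficacy endpoints will be analyzed using an MMRM model similar to the continuous secondary efficacy endpoints". It does not name the covariates.

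**The concern.** Subtracting baseline fixes the coefficient of follow-up on baseline at 1; the model never estimates it. If the true slope is below 1, the change score over-corrects chance imbalance between arms, and the excess stays in the residual. With 30 per arm, the SD of a between-arm baseline difference is √(2/30) = 0.26 baseline SDs. At a true slope of 0.5, an imbalance of that size moves the estimated treatment difference by 0.5 × 0.26 = 0.13 baseline SDs.

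Baseline NRS can absorb this only through its correlation with the endpoint's own baseline, and its range is narrow. Protocol 7.1 says "participants must have a pruritus NRS score of ≥ 7 at screening and Day 1", so baseline NRS lies between 7 and 10 and its SD cannot exceed half that range, 1.5.

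At stake is the width of the confidence intervals for the endpoints that address the secondary objective of a therapeutic effect on AD. The covariates need to be fixed before unblinding, because a covariate added afterwards could look like selection.

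**Working it through.** **Figures in the plan.** The only power statement concerns the primary endpoint, and it reproduces: 2 × (1.645 + 0.842)² / 0.72² = 23.85, rounded up to 24 per group. The documents give no SD, correlation or power for the five endpoints, so everything below rests on assumed ranges. It applies to absolute change only, not to percent change in EASI.

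**Set-up.** Let X be the endpoint's own baseline (SD 1) and N baseline NRS, with correlation ρ with X (0 to 0.4). Let Y be follow-up, with SD k and correlation r with X. Change is D = Y − X. Let b be the slope of Y on X given N, and s² the residual variance of Y given both. Then

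variance ratio (NRS only ÷ NRS plus own baseline) = 1 + (b − 1)²(1 − ρ²) / s².

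**Case 1: NRS informs follow-up only through X.** Here b = kr and s² = k²(1 − r²). For k = 1, r = 0.3, ρ = 0: 1 + 0.49/0.91 = 1.54.

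| k | r = 0.3 | r = 0.5 | r = 0.7 |
|---|---|---|---|
| 1.0 | 1.54 / 1.45 | 1.33 / 1.28 | 1.18 / 1.15 |
| 1.3 | 1.24 / 1.20 | 1.10 / 1.08 | 1.009 / 1.008 |
| 1.5 | 1.15 / 1.12 | 1.04 / 1.03 | 1.002 / 1.002 |

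(Each cell shows ρ = 0 / ρ = 0.4.) At k = 1 and r = 0.9 the ratio is 1.05 / 1.04. On the SE scale, the k = 1 row runs from √1.15 = 1.07 to √1.54 = 1.24. A ratio of 1.33 means that 120 participants give the precision of about 120/1.33 = 90.

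**Case 2: NRS also carries independent information** (partial correlation 0.2 to 0.3 with follow-up). Over the same r and ρ the excess variance is 18% to 69% at k = 1, 1% to 36% at k = 1.3 and 0% to 25% at k = 1.5. Replacing NRS with own baseline, instead of keeping both, would then cost 1/(1 − 0.2²) = 1.04 to 1/(1 − 0.3²) = 1.10 in variance.

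**Cost of the extra covariate.** At N = 120 the residual degrees of freedom go from 115 to 114 and the t critical value from 1.9808 to 1.9810. If own baseline adds nothing, the variance factor is 1 + 1/113 = 1.009 and the 95% CI is 0.45% wider. At N = 96 (df 91 to 90) it is 0.58% wider. At k = 1 the break-even is r ≈ 0.98. At k = 1.3 there is no net gain for r between 0.70 and 0.82.

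**Check by simulation.** The planned type of model was simulated: two visits, unstructured covariance, REML, common slopes, 4 × 30 participants, 19% missing at random at Week 4 (assumed), no treatment effect, ρ = 0.2, 1,500 runs. The table shows the ratio of mean squared SE for 5% gel against vehicle at Week 4.

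| Setting | Ratio |
|---|---|
| k = 1, r = 0.3 / 0.5 / 0.7 | 1.46 / 1.28 / 1.15 |
| slope 0.6 at Week 2, 0.4 at Week 4 | 1.33 |
| k = 1.3, r = 0.5 | 1.08 |
| slope 1 (k = 1.3, r = 0.77) | 0.993 |
| k = 1, r = 0.5, partial correlation 0.3 | 1.37 |

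Mean estimates were within 0.012 of zero, and rejection at nominal 5% was 3.7% to 5.5% under both models. Neither model is biased.

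**Total BSA.** Protocol 7.5 limits eligible area to 1–20% and adds that "participants with a ratio of BSA of intended area over total BSA of less than 80% on Day 1 will be excluded". Total BSA at entry is therefore at most about 20/0.8 = 25%, while follow-up has no limit. Follow-up SD may exceed baseline SD, and a slope near 1 is plausible.

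**The case against.** The stakes are modest. The analysis is valid, the MCPMod decision uses none of these endpoints, and no success rule is attached to them. That stands: this is an improvement in efficiency and does not correct an error.

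The larger figures deserve caution, and this stands too. The 69% in Case 2 needs r = 0.3, ρ = 0.4 and partial correlation 0.3. These imply a correlation of 0.3 × 0.4 + 0.3 × √(0.91 × 0.84) = 0.38 between baseline NRS and follow-up, above the 0.30 for the endpoint's own baseline. That is hard to credit for a covariate confined to 7–10. The simulated gains are also somewhat below the closed form (1.28 against 1.32 at r = 0.5, ρ = 0.2), and a high correlation such as 0.9 leaves only 4% to 5% at k = 1. Near slope 1 the net effect is nil or a very small loss.

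Protocol 9.3.1 could be read as intending each endpoint's own baseline, with the SAP 13.2 sentence carried over from the primary analysis. That may explain the wording, but the SAP text is explicit and names NRS.

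No gain has been calculated for percent change in EASI or for vIGA, which entry restricts to 2 or 3. For these the case is only that the covariate costs about one degree of freedom and makes the specification consistent.

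**Conclusion.** The concern holds. As written, SAP 13.2 leaves out the endpoint's own baseline for five non-NRS secondary endpoints and fixes its slope at 1 through the change score. For absolute change with equal SDs and r from 0.7 to 0.3, the resulting variance is 15% to 54% larger than with own baseline added in the closed form. The simulated model gave 15% to 46% at ρ = 0.2. The excess shrinks when follow-up is more variable than baseline and vanishes at slope 1, so total BSA may gain nothing. The worst case for the change is a CI about 0.5% wider. These sizes depend on correlations that the documents do not supply; the direction depends only on the slope not being near 1. Validity and the NRS analyses are not in question.

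**What to change.** Before unblinding, amend SAP 13.2 so that the model for 5-D, EASI, total BSA, DLQI and POEM reads: *baseline NRS and the baseline value of the endpoint being analysed as covariates, each with one slope common to all visits*. Keep baseline NRS, because it may carry information of its own, most obviously for 5-D, which SAP 5.7.5 describes as a "validated questionnaire used in clinical trials to assess 5 dimensions of background itch". Leave the NRS endpoints as they are. In SAP 13.3, state that the vIGA model also includes baseline vIGA. The change is to SAP wording only: no new data, and about one residual degree of freedom per model (115 to 114 at N = 120). A separate baseline slope for each of Weeks 2 and 4 would cost two and is not proposed.
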